## 5. STUDY POPULATION

### 5.1. Study Participants

ALS patients from main ADORE study.

### 5.2. Inclusion Criteria

All patients:

1. who completed the full study period in the main ADORE study (FAB122-CT-2001);
2. whom the investigator has no concern and judges tolerable receiving treatment with FAB122 from a risk and benefit point of view;
3. a female subject should not be able to become pregnant up to 30 days after the last dose of FAB122 and needs to meet at least one of the following criteria:
  - female subject who is not of reproductive potential is eligible without requiring the use of contraception. A woman is considered not having childbearing potential when becoming post-menopausal unless permanently sterile. Permanent sterilisation methods include hysterectomy, bilateral salpingectomy and bilateral oophorectomy. A postmenopausal state is defined as no menses for 12 months without an alternative medical cause.
  - female who is of reproductive potential and has a negative pregnancy test at baseline and is non-lactating. A female subject who is of reproductive potential agrees to use (or have their partner use) adequate birth control methods starting from the time of consent through 30 days after the last dose of study therapy. Longer periods of birth control may be required per local requirements. Acceptable methods of birth control include combined (estrogen and progestogen containing) hormonal contraception associated with inhibition of ovulation (oral, intravaginal, transdermal), progestogen-only hormonal contraception associated with inhibition of ovulation (oral, injectable, implantable), intrauterine device in place for ≥3 months, intrauterine hormone-releasing system, bilateral tubal occlusion or vasectomised partner.
4. a male patient must:
  - agree he will not donate sperm during the period he will be using FAB122 AND use a condom during sexual intercourse with pregnant or non-pregnant women of childbearing potential (WOCBP) partner even if he is vasectomized until 104 days after the last dose.
  - in addition WOCBP partner of the male patient must use the following acceptable methods of birth control during the study and until 104 days after the last dose: combined (estrogen and progestogen containing) hormonal contraception associated with inhibition of ovulation (oral, intravaginal, transdermal), progestogen-only hormonal contraception associated with inhibition of ovulation (oral, injectable, implantable), intrauterine device in

---

place for ≥3 months, intrauterine hormone-releasing system, bilateral tubal occlusion or vasectomised partner;

5. providing informed consent.

will be eligible and enrolled.

### **5.3. Exclusion Criteria**

Patients who meet any of the following criteria, will not be eligible for the study:

1. Patient who has a medical condition (e.g. cardiac, pulmonary, gastrointestinal, musculoskeletal, or psychiatric illness) or personal circumstances which, in the opinion of the investigator, will make initiation or continuation of treatment with FAB122 not tolerable for them from a risk and benefit point of view.
2. Patient who discontinued study drug prematurely in the double-blind phase of the study (ADORE Study) for safety reasons.
3. Patient who has received any other investigational drug within the period between last visit of the main study and first visit of the extension study (i.e. another trial, managed access program, open label extension or early access program)
4. History of known hypersensitivity to edaravone or to any of the excipients.

For patients who do not take FAB122 but are only followed up by phone, only inclusion criteria #1 and #5 will apply.

## 6. STUDY PROCEDURES

All the study procedures are presented in the following table:

**Table 1: Study Scheduled Visits**

	Baseline	
	V1 D1 W0	V2-N End of Trial Every 3 months (±1 week)
Administrative procedures		
ICF	X	
ICF for FBR	X	
In/exclusion assessment	X	
Dispensing study medication	X	X
Clinical Procedures		
Physical examination	X	X 
Vital Signs	X	X
Weight	X	X
12-lead ECG	X	X 
Neurological examination	X	X 
(S)AE monitoring	X	X
Prior/Concomitant medication	X	X
Laboratory procedures		
Chemistry  /Haematology  /Urinalysis 	X	X
Vitamin B6 monitoring 	X	X
Urine Pregnancy Test	X	X
Blood/urine sampling for biomarkers 	X	X 
Blood sampling for genotyping for FBR (if consented)	X	
ALS evaluation procedures		
ALSFRS-R	X	X
SVC	X	X
ALSAQ-40	X	X
EQ-5D-5L/VAS	X	X
ECAS	X	X 
King's staging system and MiToS	X	X
Cost questionnaire	X	X
Vital Status Follow Up 		X
Study Drug Administration	X	

V=visit

1. Baseline visit is V6 or V8 of the main study. In case the ADOREXT study is not fully set up at the time of subject's finalization in the main ADORE study, baseline visit could take place up to 6 weeks after finalization. For patients who do not take FAB122 but are only followed up by phone, only ICF will be obtained.

2. Hematology: hematocrit, hemoglobin, RBC (red blood cell count & parameters), WBC (white blood cell count inclusive differential count), platelet (thrombocytes). Biochemistry: total protein, alkaline phosphatase, AST (aspartate transaminase), ALT (alanine transaminase), GGT (Gamma-glutamyl transpeptidase), direct and total bilirubin, blood urea nitrogen (BUN), creatinine (serum), sodium, potassium, chloride, calcium, bicarbonate, LDH (lactate dehydrogenase), CK (creatine kinase), eGFR (estimated glomerular filtration rate), uric acid and fasting glucose, activated partial thromboplastin time (aPTT), prothrombin time (PTT) and fibrinogen.. Urinalysis or dipstick: Blood, Glucose, Protein, Specific gravity, Ketone, pH, Nitrite, Leukocytes, Bilirubin, Urobilinogen, Microscopic exam, if abnormal results are noted.
3. PLP levels will be monitored and, if necessary, supplementation of vitamin B6 (pyridoxine (100 mg/day)) will be prescribed.
4. When patient withdraws consent, is not able to attend the study visits any more or is discontinued.
5. Only for patients not taking IMP, phone contact. For patients who do not take FAB122 but are only followed up by phone, only vital status will be collected. The rest of assessments will not be done.
6. Every 6 months.
7. Blood biomarkers: neurofilament light chain (NFL). Serum creatinine and serum creatine kinase will be measured in biochemistry lab testing. Urine biomarkers: 8-hydroxy-2'-deoxyguanosine (8-OhdG), extracellular domain of neurotrophin receptor p75 (p75ECD).
8. Every 12 months.

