#### **Follow up of patients unable to attend to one onsite study visit**

In case that, on an ad hoc basis, due to ALS progression, the subject is not able to attend the clinic or perform specific testing such as SVC, at least ALSFRS-R score and adverse events will be collected (if necessary by telephone). Study medication will be provided to the patient as detailed in section 7.1.4. On site visit for key safety assessments needs to be performed as soon as possible (max. up to 6 months from last visit) to assess vital signs and perform physical exam, ECG and laboratory assessments.

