#### **Follow up of patients unable to attend to more than one onsite study visit**

If, in the judgment of the site Investigator, the participant cannot reasonably be expected to travel to the clinic, the minimum data required to continue on study medication are laboratory tests (hematology, biochemistry and urinalysis or dipstick as per local lab standards), adverse event reporting and ALSFRS-R.

The monitoring of ALSFRS-R and AEs may continue by telephone according to the nominal visit schedule.

Laboratory samples for safety assessments may be obtained through a local laboratory, and results will be reviewed by the site investigator and the medical monitor. These data are to be obtained at least every 6 months until the patients withdraw, reaches the endpoint or the study completes, whichever occurs first.

In case the site has an established procedure in place to perform visits at the home of the participant, the sponsor will assess the adequacy of the procedure in order to be used in the ADOREXT study. If the procedure is deemed adequate to guarantee patient's safety and the integrity of the data, home visits by the delegated site staff can be performed.

---

If the patient becomes unfit for travel, this information and the procedures to be followed to ensure the safety assessment of the patients must be documented in the source data. If no accommodations can be made for adequate safety monitoring, patients will be withdrawn from study medication.

The following sections provide details regarding the procedures to be performed at each study visit:

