## 6.5. Early Discontinuation/Withdrawal of Participants

Subjects may withdraw consent at any time for any reason or be discontinued from the extension trial at the discretion of the investigator should any untoward effect occur. In addition, a subject may be withdrawn by the investigator or the Sponsor if enrolment into the trial is inappropriate, the trial plan is violated, or for administrative and/or safety reasons.

In this trial, a subject may discontinue from treatment but continue to participate in the regularly scheduled activities, as long as the subject does not withdraw consent.

A subject must be discontinued from the trial for any of the following reasons:

- The subject withdraws consent.
- The subject has a medical condition or personal circumstances which, in the opinion of the investigator and/or Sponsor, places the subject at unnecessary risk if participation in the trial is continued.

A subject must be discontinued from study treatment (but should continue to be monitored in the study) for any of the following reasons:

- 1) Key safety assessment cannot be performed.
- 2) The subject becomes pregnant during the study.
- 3) The subject's investigator considers it is in the best interest of the subject to discontinue.
- 4) Serious adverse event considered related to the IMP
- 5) Severe Neurotoxicity considered related to the IMP
- 6) Any other severe adverse event considered related to the IMP at the discretion of the investigator.
- 7) Acute renal failure (creatinine clearance of less than 30 mL/min)
- 8) Severe liver disorder defined as:
  - a. ALT/AST  $\geq$  3xULN and bilirubin  $\geq$  2xULN (>35% direct bilirubin).
  - b. ALT/AST  $\geq$  8xULN.
  - c. ALT/AST  $\geq$  3xULN and with symptoms believed to be related to liver injury or hypersensitivity.
  - d. ALT/AST  $\geq$  3x baseline ALT/AST and with symptoms believed to be related to liver injury or hypersensitivity.
  - e. ALT/AST  $\geq$  5xULN and ALT/AST  $<$  8xULN that persists more than two weeks.
- 9) Acute lung injury with pyrexia, cough, dyspnoea and chest X-ray abnormality.
- 10) Rhabdomyolysis.
- 11) Disseminated intravascular coagulation (DIC).
- 12) Hypersensitivity reaction
- 13) Anaphylactic reaction/shock
- 14) Thrombocytopenia
  - a. Platelets  $<$  20  $10^9/L$  or  $>$  1000  $10^9/L$
  - b. Platelets between 20 and 50  $10^9/L$  if in the investigator judgement the patient present risk of any kind of bleeding or haemorrhage.

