#### **5.5.2 Secondary analysis**

##### **5.5.2.1 Overall Survival and ‘Survival Time’**

Time to event endpoints for overall survival and survival time definitions are reported in Section 4.2. Patients who early terminated the ADOREXT study for reasons different from death will be considered as still alive and with no respiratory insufficiency event at the time of study discontinuation, unless otherwise specified in the survival follow-up CRF form. Endpoints will be derived by combining the survival data from ADORE and ADOREXT.

Descriptive statistics including median, Q1/Q3 quartiles with 95% confidence intervals will be tabulated. Endpoints will be also summarized with the use of the Kaplan-Meier method.

The difference between the groups randomized in ADORE to FAB122 and placebo will be evaluated descriptively by means of a stratified log rank test. Hazard ratios and 95% confidence intervals will be estimated with the use of a stratified Cox proportional-hazards regression model with treatment group as the sole explanatory variable.

The difference between the groups will also be assessed using restricted mean survival time (RMST) analysis. Considering the duration of the ADOREXT study, the RMST will be performed up to the largest observation time from the pooled ADORE and ADOREXT data, adjusting for the stratification variables.

Randomization strata from ADORE study will be used for the stratified analysis. No adjustment will be performed for the treatment cross over following enrollment in ADOREXT study.

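### Table 1 footnote 4 ends the trial for patients who can no longer attend visits, while Section 6 keeps them in; a site that follows the footnote may create progression-linked censoring in the survival analyses.

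*Protocol*

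**What the plan says.** **Table 1, footnote 4.** The footnote hangs on the End of Trial label in the header of the follow-up visit column. It gives three triggers: "When patient withdraws consent, is not able to attend the study visits any more or is discontinued".

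**Protocol Section 6, text after Table 1.** A patient who misses one visit because of progression still contributes ALSFRS-R and adverse events, by telephone if need be. For a patient who cannot be expected to travel again, a minimum data set allows study medication to continue, and "The monitoring of ALSFRS-R and AEs may continue by telephone according to the nominal visit schedule". Local laboratories are allowed, as are home visits where the sponsor accepts the site's procedure. Where safety monitoring cannot be arranged, the consequence concerns treatment only: "If no accommodations can be made for adequate safety monitoring, patients will be withdrawn from study medication".

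**Protocol Section 6.5.** Stopping treatment is kept apart from leaving the trial: "a subject may discontinue from treatment but continue to participate in the regularly scheduled activities", as long as consent stands. The list introduced by "A subject must be discontinued from the trial for any of the following reasons" has two entries: withdrawal of consent, and a medical condition or personal circumstances that make continued participation an unnecessary risk. Inability to attend is not on it.

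**Vital-status calls.** Table 1, footnote 5, gives telephone contact to patients not taking IMP, without further condition. Section 6.4 names only patients unwilling to receive or continue treatment and those who stopped in ADORE for safety reasons.

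**SAP 5.5.2.1.** Patients who leave ADOREXT early for a reason other than death "will be considered as still alive and with no respiratory insufficiency event at the time of study discontinuation", unless the survival follow-up CRF form states otherwise. Both time-to-event endpoints run from the start of treatment in ADORE (SAP 4.2) and pool the two studies.

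**The concern.** Footnote 4 and the text after the table give sites different instructions for the same patients. In ALS, losing the ability to travel is usually a sign of progression. A patient closed out for that reason probably has a higher hazard of death or respiratory insufficiency than the patients who stay under observation.

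Censoring at discontinuation is ordinary practice and unbiased when the reason is unrelated to prognosis. Here the reason is related to it. Kaplan-Meier estimates, and the median and quartiles read from them, would then describe a healthier group than the one enrolled.

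The SAP has no analysis that would show this. Section 5.5.2.1 gives no sensitivity analysis by reason for censoring. The censoring-weight method named in Protocol 11.3.4 was meant for treatment switching and is not carried into the SAP. The safeguard that remains is the survival follow-up form, and the documents disagree on which patients receive the calls that would feed it.

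**Working it through.** **Step 1: the texts side by side, for a patient who can no longer travel and has not withdrawn consent.**

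| Source | Consequence |
|---|---|
| Table 1, footnote 4 | End of Trial |
| Section 6, text after Table 1 | Stays in; telephone, local laboratory or home visit |
| Section 6, if monitoring cannot be arranged | Off study medication; leaving the trial is not mentioned |
| Section 6.5 | Not a listed reason for mandatory trial discontinuation |
| Footnote 5 | Vital-status calls if not taking IMP |
| Section 6.4 | Not named for vital-status calls on this ground |
| SAP 5.5.2.1 | If closed out: censored as event-free, unless the survival form says otherwise |

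Footnote 4 is the outlier.

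**Step 2: size.** The documents state no figure to reproduce and give no rates, so every input here is an assumption:
- event hazard while able to travel, h = 0.15 to 0.25 per year;
- rate of becoming unable, q = 0.20 to 0.35 per year, which is 1 − exp(−q) = 18% to 30% within a year before allowing for competing events;
- hazard multiplied by k = 2 to 4 once unable;
- everyone able to travel at ADOREXT entry.

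True event-free survival at time t after entry:

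S(t) = exp(−(h+q)t) + q[exp(−kht) − exp(−(h+q)t)] / (h + q − kh)

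If every newly unable patient is closed out and no later status is recorded, only patients able to travel remain at risk, so Kaplan-Meier targets exp(−ht).

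- Low end (h = 0.15, q = 0.20, k = 2, t = 1): S = 0.7047 + 0.20 × (0.7408 − 0.7047)/0.05 = 0.849. Kaplan-Meier: exp(−0.15) = 0.861. Overstatement 1.1 points (1.15 unrounded).
- High end (h = 0.25, q = 0.35, k = 4, t = 1): S = 0.5488 + 0.35 × (0.3679 − 0.5488)/(−0.40) = 0.707. Kaplan-Meier: exp(−0.25) = 0.779. Overstatement 7.2 points.

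If a fraction f is closed out, the unable group under observation shrinks to (1 − f) of its size. Kaplan-Meier then targets the exponential of minus the integrated hazard in those still observed, integrated numerically:

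| Fraction closed out | Overstatement one year after ADOREXT entry |
|---|---|
| 0% | 0 |
| 25% | 0.3 to 1.5 points |
| 50% | 0.5 to 3.2 points |
| 100%, no later status | 1.1 to 7.2 points |

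A second set of assumed monthly rates (death hazard 0.01 while able, 0.03 to 0.06 once unable; 0.02 to 0.04 becoming unable) gives 1.0 to 3.8 points at 12 months with half closed out and 2.2 to 9.0 with all. With equal hazards in the two states the bias is zero. The direction therefore follows from the higher hazard; the size follows from the inputs.

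**Step 3: the SAP's time scale.** Patients enter ADOREXT after 48 to 72 weeks in ADORE (Protocol 2.1). Footnote 4 therefore governs at most about 4 of the first 52 weeks on the SAP clock. With t = 4/52, the all-closed-out gap is 0.009 points (low end) and 0.074 points (high end). Multiplying by the share event-free at week 48, exp(−0.15 × 48/52) = 0.871 and exp(−0.25 × 48/52) = 0.794, gives about 0.01 and 0.06 points. Any material effect on the SAP's curves comes later.

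**The case against.** The strongest reply is that the detailed text all points one way. Section 6 sets out how to continue, Section 6.5 lists who must leave and omits this reason, and footnote 5 on its face covers anyone off IMP. Footnote 4 sits on a shared column header and could mean only when the End of Trial assessments are done. This lowers the chance that sites close patients out, and it is why the range starts at zero. It does not remove the conflict: the footnote groups inability to attend with withdrawal of consent, makes no reference to the telephone route, and nothing in the text confirms the narrower reading.

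It is also true that the primary endpoint is TEAEs, that the survival comparison is descriptive, and that the study has ended early, so rewording alone recovers nothing. These points limit the consequence and change the remedy.

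A reader might infer more than the documents support:
- **That one-year survival as reported will be 1 to 7 points too high.** That needs every such patient closed out, no later status on any of them, and a clock starting at ADOREXT entry. The SAP clock starts in ADORE.
- **That closed-out patients will be censored as event-free.** They can be; the SAP gives way to the survival follow-up form.
- **That the bias differs between sites or favours one arm.** Nothing in the documents shows how close-out varied by site or by original arm.

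**Conclusion.** The inconsistency is real and stands in the current text. If sites followed footnote 4, the resulting censoring is likely informative and makes absolute overall survival and survival time look too favourable.

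The size is unknown. Under the assumed rates it lies between 0 and 7.2 points one year after ADOREXT entry, among patients who entered, with 0.5 to 3.2 points if half of the newly unable are closed out. On the SAP clock it is negligible at one year and appears only at later times. The effect on the log-rank test, hazard ratio or RMST difference between original arms cannot be signed, because it depends on whether close-out differed by arm.

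The conclusion rests on one assumption from outside the documents' figures: that patients unable to travel have a higher event hazard than those who can.

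**What to change.** 1. **Protocol.** Reconcile footnote 4 with the text after Table 1 and with Section 6.5, and footnote 5 with Section 6.4. The rule for treatment is the sponsor's to set. For data collection, state that inability to attend does not by itself end collection of vital status and respiratory insufficiency in patients who have not withdrawn consent, nor of ALSFRS-R and adverse events where the telephone route applies.
2. **Data.** Because the study ended early, use the discontinuation reasons that SAP 5.4.3 already tabulates to identify patients closed out on this ground, and obtain their last known vital status, consent permitting. The CRF is not among the documents, so whether it codes this reason separately has to be checked.
3. **SAP.** Add to 5.5.2.1 a sensitivity analysis of overall survival and survival time by reason for censoring, and report by original arm how many patients were censored for inability to attend.

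The cost is a few sentences of wording, a little extra telephone follow-up and one additional analysis. The telephone route is already in the protocol.

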#### **Follow up of patients unable to attend to one onsite study visit**

In case that, on an ad hoc basis, due to ALS progression, the subject is not able to attend the clinic or perform specific testing such as SVC, at least ALSFRS-R score and adverse events will be collected (if necessary by telephone). Study medication will be provided to the patient as detailed in section 7.1.4. On site visit for key safety assessments needs to be performed as soon as possible (max. up to 6 months from last visit) to assess vital signs and perform physical exam, ECG and laboratory assessments.

#### **Follow up of patients unable to attend to more than one onsite study visit**

If, in the judgment of the site Investigator, the participant cannot reasonably be expected to travel to the clinic, the minimum data required to continue on study medication are laboratory tests (hematology, biochemistry and urinalysis or dipstick as per local lab standards), adverse event reporting and ALSFRS-R.

The monitoring of ALSFRS-R and AEs may continue by telephone according to the nominal visit schedule.

Laboratory samples for safety assessments may be obtained through a local laboratory, and results will be reviewed by the site investigator and the medical monitor. These data are to be obtained at least every 6 months until the patients withdraw, reaches the endpoint or the study completes, whichever occurs first.

In case the site has an established procedure in place to perform visits at the home of the participant, the sponsor will assess the adequacy of the procedure in order to be used in the ADOREXT study. If the procedure is deemed adequate to guarantee patient's safety and the integrity of the data, home visits by the delegated site staff can be performed.

---

If the patient becomes unfit for travel, this information and the procedures to be followed to ensure the safety assessment of the patients must be documented in the source data. If no accommodations can be made for adequate safety monitoring, patients will be withdrawn from study medication.

The following sections provide details regarding the procedures to be performed at each study visit:

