### 6.3. Rest of visits

Every 3 months and up to the product is marketed, subjects will attend the study site and the following procedures will be performed:

- Review ongoing concomitant medications.
- Complete physical examination (every 6 months).
- Neurological examination (every 6 months).
- Weight.
- Vital signs measured with the subject in a supine/semi-supine position (for at least 5 minutes prior), including blood pressure, pulse rate, respiratory rate, pulse oximetry and temperature.
- Standard 12-lead ECG (subject should be in a supine/semi-supine position for at least 5 minutes prior to assessment) (every 6 months).
- Blood samples for routine clinical labs (clinical chemistry, haematology). See table 2 for lab assessments.
- Urine samples for urinalysis or dipstick testing.
- Blood sampling for biomarkers: neurofilament light (NFL) (every 12 months).
- Urine collection for biomarkers: urinary extracellular domain of neurotrophin receptor p75 (Urinary P75ECD) and oxidative stress biomarker 8-hydroxyguanosine (8-OHdG) (every 12 months).
- Urine pregnancy test only in women of childbearing potential.
- Plasma pyridoxal 5'-phosphate (PLP) levels, and, if necessary, vitamin B6 supplements (pyridoxine (100 mg/day)) will be prescribed.
- ALS evaluation procedures: ALSFRS-R, Slow Vital Capacity (SVC), ALSAQ-40, EQ-5D-5L, VAS, King's staging system and, MiToS.
- Adverse Events monitoring.
- ECAS (every 6 months).
- Vital status (tracheostomy or initiation of non-invasive ventilation for more than 20 hours a day for more than 10 consecutive days) / Date of death. Cost questionnaire
- Dispense study medication

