### **9.8. Pregnancy**

According to the recommendations on the CTFG contraception guidance, highly effective contraception measures are required for this study. All females patients who are of reproductive potential will be requested to use (or have their partner use) or practicing adequate birth control methods starting from the time of consent through 30 days after the last dose of study therapy. Longer periods of birth control may be required per local requirements. Acceptable methods of birth control include combined (estrogen and progestogen containing) hormonal contraception associated with inhibition of ovulation (oral, intravaginal, transdermal), progestogen-only hormonal contraception associated with inhibition of ovulation (oral, injectable, implantable), , intrauterine device in place for  $\geq 3$  months, intrauterine hormone-releasing system, bilateral tubal occlusion or vasectomised partner.

If a patient becomes pregnant during the study or within the safety follow-up period defined in the protocol, the Investigator is to stop dosing with study drug(s) immediately.

A pregnancy as such is not an AE, however, it must be reported to the Sponsor within 24 hours of knowledge of the event completing a Pregnancy Reporting Form.

Female patients will be instructed to notify the investigator immediately if they become pregnant during the study. Male patients will be instructed to notify the investigator immediately if their partner becomes pregnant. Pregnant patients will be withdrawn from further study treatment. The patients will also be instructed to report pregnancies discovered after the last visit, if they believe that conception occurred during their participation in the study.

The pregnant patient or partner will be followed until the end of the pregnancy. Any complication during the pregnancy should preferably be reported as an AE. The outcome of the pregnancy must be reported on the Pregnancy Reporting Form. Any spontaneous abortion, stillbirth, birth defect/congenital anomaly, death, or other serious infant condition must be reported and followed up as an SAE. If the pregnancy outcome meets seriousness criteria the both the SAE form and pregnancy form should be forwarded.

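### The minimum data for keeping patients who cannot travel on FAB122 leave out the urine pregnancy test for women of childbearing potential

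*Protocol*

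**What the plan says.** Section 6 of the protocol has a subsection for patients who miss more than one on-site visit and cannot reasonably be expected to travel. It states that "the minimum data required to continue on study medication are laboratory tests (hematology, biochemistry and urinalysis or dipstick as per local lab standards"; the list then closes with adverse event reporting and ALSFRS-R. On timing, "The monitoring of ALSFRS-R and AEs may continue by telephone according to the nominal visit schedule", and for the required data as a whole, "These data are to be obtained at least every 6 months until the patients withdraw, reaches the endpoint or the study completes". Laboratory samples may be taken through a local laboratory.

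The ordinary schedule is fuller. Table 1 has a separate row for the urine pregnancy test, marked at baseline and at every 3-monthly visit with no footnote reducing its frequency. Section 6.3 lists it as a separate item: "Urine pregnancy test only in women of childbearing potential".

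Pregnancy has consequences for treatment. Section 6.5 makes it the second of the mandatory reasons to discontinue study treatment, and Section 9.8 says that "the Investigator is to stop dosing with study drug(s) immediately". Section 9.8 also relies on the patient: "Female patients will be instructed to notify the investigator immediately if they become pregnant during the study". It adds: "A pregnancy as such is not an AE, however, it must be reported to the Sponsor within 24 hours".

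**The concern.** The subsection sets the condition on which a patient who cannot travel may stay on drug. A site that meets this condition exactly can go on supplying FAB122 to a woman of childbearing potential without testing her for pregnancy, for as long as the remote arrangement lasts. If she has not recognised a pregnancy, nothing in the listed data is designed to reveal it, and the mandatory stop is not triggered.

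For patients who attend the clinic, the sponsor scheduled a test every 3 months on top of contraception and self-report. The protocol gives no reason for relying on those two alone once visits move to telephone and local laboratory while dosing continues. What is at stake is participant safety; no estimate is at risk.

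**Working it through.** The plan states no figure on this point, so the check compares texts and then counts scheduled tests.

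**Step 1. Does any item in the remote minimum include the test?**

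| Place in protocol | What it shows |
|---|---|
| Section 6, remote minimum | Laboratory tests are itemised in brackets: haematology, biochemistry, urinalysis or dipstick. No pregnancy test. |
| Table 1, rows | The pregnancy test has its own row, apart from the chemistry/haematology/urinalysis row. |
| Table 1, footnote 2 | "Urinalysis or dipstick: Blood, Glucose, Protein, Specific gravity, Ketone, pH, Nitrite, Leukocytes, Bilirubin, Urobilinogen, Microscopic exam, if abnormal results are noted" – no pregnancy item. |
| Table 2, urinalysis/dipstick column | No pregnancy item. |
| Section 6.3 | Urinalysis or dipstick is one item, the pregnancy test another. |

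The urinalysis item therefore does not cover it. Adverse event collection does not by its terms cover it either, because Section 9.8 states that a pregnancy in itself is not an adverse event.

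**Step 2. Does another clause require the test for these patients?**

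- Contraception (Sections 5.2 and 9.8) lowers the risk but detects nothing. The negative test in Section 5.2 is at baseline only.
- Self-report (Section 9.8) works only once the patient knows she is pregnant.
- Home visits depend on the site already having a procedure that the sponsor finds adequate.
- The remote subsection withdraws the drug if adequate safety monitoring cannot be arranged, and Section 6.5, reason 1, stops treatment if a key safety assessment cannot be done. Neither names the test. The one place that spells out key safety assessments, the subsection on a single missed visit, names vital signs, physical examination, ECG and laboratory assessments.
- Dispensing is not a guaranteed checkpoint: Section 7.1.3 allows delivery to the home where needed and locally permitted.

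Each clause gives some cover. None requires a test.

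**Step 3. Count per remote patient-year.**

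- Visit schedule (Table 1, Section 6.3): 12 months / 3 months = 4 tests.
- Named in the remote minimum: 0.
- Remote laboratory draws, at the minimum frequency: 12 / 6 = 2.
- With the test added to those draws: at least 2, at most about 6 months apart, against about 3 months under Table 1.
- With optional home tests at the two intervening telephone contacts: 2 + 2 = 4, the Table 1 frequency.

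**Step 4. Is it feasible remotely?** The minimum also omits vital signs, ECG, and physical and neurological examination. Section 8.2.1 requires qualified personnel for the examinations, so leaving them out for a patient who cannot travel is understandable. The pregnancy test can use a urine sample that the minimum already asks for.

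**The case against.** The strongest reply is that the list is a floor. It sets what must be available for dosing to continue and does not expressly cancel Table 1 or Section 6.3. A reader might infer that the protocol abolishes pregnancy testing for remote patients; the text does not say so, and that reading is not adopted here. What stands is narrower: the test is not a condition for staying on drug.

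Second, a site could combine the clauses. Laboratory assessments count among the key safety assessments, and Table 1 puts the pregnancy test under its laboratory heading. The remote subsection also requires the arrangements for safety assessment to be documented in source. This is a fair reading, and a careful site may act on it. However, the remote minimum specifies its laboratory tests in brackets, and another site can as reasonably stop at that list.

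Third, the group is small. Section 2.1 of the protocol places ALS mostly at 40–60 years, and these women must also have completed ADORE and then become unable to travel. That is accepted. A reader might multiply 4 tests a year by the planned period of about 3 years and report 12 tests lost against none required. That figure is only an upper bound: patients become remote after baseline, sites may test anyway, and the SAP (Sections 2.1 and 6) reports that the study ended early.

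Fourth, a reader might extend the point to vitamin B6 (PLP), which the remote minimum does not name either. The documents do not support calling it omitted. Table 2 lists vitamin B6 in its chemistry column, so the biochemistry item can be read to include it.

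**Conclusion.** The point holds in limited form. The minimum data for continuing FAB122 in patients who cannot travel do not include the pregnancy test, although pregnancy is a mandatory stop, and the remaining safeguards cover the gap only in part. The size is 4 scheduled tests against none named per remote patient-year, for women of childbearing potential only.

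This rests on two assumptions: that the bracketed laboratory list is read as complete, and that at least one woman of childbearing potential reaches the remote arrangement while on drug. The documents do not say how many would, nor how often an unrecognised pregnancy would occur, so no harm rate is claimed. No endpoint, analysis set or estimate is affected. It is a low-priority improvement, and early termination leaves it little practical reach in this study.

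**What to change.** In the Section 6 subsection on patients unable to attend more than one on-site visit, add to the bracketed laboratory tests: urine pregnancy test (women of childbearing potential). Perform it on the urine sample already required at each remote laboratory draw, so at least every 6 months. A home test at the intervening telephone contacts can be offered where feasible but need not be required: it is self-reported and may need a caregiver's help.

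The cost is about 2 extra urine tests per remote patient-year in this subgroup, with no additional sample or visit. If no patient remains on treatment, carry the wording into any later remote follow-up text for FAB122.
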